Appendix 4. ABBREVIATED PRESENTATION OF RECIST VERSION 1.1 GUIDELINES

A modification to RECIST 1.1 has been made to account for the possibility of temporary changes resulting from the potentially beneficial treatment responses of tumor necrosis, cavitation or flare response.

Categorizing Lesions at Baseline

Measurable Lesions

- Accurately measured in at least one dimension.
- When assessed by CT or MRI, longest diameter at least 10 mm or greater (slice thickness 5-8 mm), measured in the axial plane. If the slice thickness is greater than 5 mm (including any inter-slice gap), the longest diameter must be at least twice the slice thickness.
- Malignant lymph nodes with a short axis (defined as the largest measurement perpendicular to the longest diameter of the lesion) 15 mm or greater when assessed by CT or MRI.

The shortest axis is used as the diameter for malignant lymph nodes, longest axis for all other lesions.

Non-Measurable Disease

- Lesions too small to be considered measurable (including nodes with short axis between 10 and 14.9 mm) or truly non-measurable disease such as pleural or pericardial effusions, ascites, inflammatory breast disease, leptomeningeal disease, lymphangitic involvement of skin or lung, and abdominal masses identified by physical exam that are not measurable by reproducible imaging techniques.
- Bone disease is non-measurable with the exception of soft tissue components that can be evaluated by CT or MRI and meet the definition of measurability at baseline.
- Previously irradiated lesions (or those patiented to other local treatment) are non-measurable unless it they have progressed since completion of treatment.

Normal Lesions

• Non-malignant simple cysts should not be recorded either as target or non-target disease. Cystic lesions thought to represent cystic metastases can be measurable lesions, if they meet the specific definition above.

• Lymph nodes with short axis <10 mm are considered normal and should not be followed as disease

Tumor Assessments

All sites of disease must be assessed at baseline. Baseline assessments should be done as close as possible prior to study start. All required scans must be done within the window of time specified in the Schedule of Assessments prior to treatment. If the baseline assessment is inadequate, subsequent statuses generally should be indeterminate.

The determination of whether lesions are measurable is performed only at baseline. "Measurable" at baseline means eligible for selection as target lesions, and thus for quantitative assessment throughout the trial. Once selected as a target lesion, a lesion remains target throughout the trial.

Target Lesions

All measurable lesions up to a maximum of 2 lesions per organ, 5 lesions in total, representative of all involved organs, should be identified as target lesions at baseline. Target lesions should be selected on the basis of size (longest lesions) and suitability for accurate repeated measurements. Record the longest diameter for each lesion, except in the case of pathological lymph nodes for which the short axis should be recorded. The sum of the diameters (longest for non-nodal lesions, short axis for nodal lesions) for all target lesions at baseline will be the basis for comparison to look for partial response at later assessments.

- If 2 target lesions coalesce the longest diameter measurement of the coalesced mass is used. If a large target lesion splits, the sum of the parts is used.
- Measurements for target lesions that become small should continue to be recorded. If a target lesion becomes too small to measure, 0 mm should be recorded if the lesion is considered to have disappeared; otherwise a default value of 5 mm should be recorded.
- When nodal lesions decrease to <10 mm (normal), the actual measurement should still be recorded.

Non-Target Lesions

All non-measurable disease is non-target. All measurable lesions not identified as target lesions are also included as non-target disease. Measurements are not required but rather qualitative evaluations of status will be recorded. Multiple non-target lesions in one organ may be recorded as a single item on the CRF (e.g., 'multiple liver metastases').

Objective Response Status at Each Evaluation

Disease sites must be assessed using the same technique as baseline, including consistent administration of contrast. If not, subsequent objective statuses may be indeterminate.

Target Disease

- Complete Response (CR): Complete disappearance of all target lesions with the exception of nodal disease. All target nodes must decrease to normal size (short axis < 10 mm). All target lesions must be assessed.
- Partial Response (PR): Greater than or equal to 30% decrease under baseline of the sum of diameters of all target measurable lesions. The short diameter is used in the sum for target nodes, while the longest diameter is used in the sum for all other target lesions. All target lesions must be assessed.
- Stable Disease (SD): Does not qualify for CR, PR or Progression. All target lesions
 must be assessed. Stable can follow PR only in the rare case that the sum increases
 by less than 20% from the nadir, but enough that a previously documented 30%
 decrease no longer holds.
- Progressive Disease (PD): 20% increase in the sum of diameters of target measurable lesions above the smallest sum observed (over baseline if no decrease in the sum is observed during therapy) with a minimum absolute increase of 5 mm.
- Indeterminate: Progression has not been documented, and
 - o one or more target lesions have not been assessed,
 - o or assessment methods used were inconsistent with those used at baseline and impaired assessment,
 - o or one or more target lesions cannot be measured accurately (e.g., poorly visible unless due to being too small to measure),
 - or one or more target lesions were excised or irradiated and have not reappeared or increased.

Non-Target Disease

- CR: Disappearance of all non-target lesions and normalization of tumor marker levels. All lymph nodes must be 'normal' in size (<10 mm short axis).
- Non-CR/Non-PD: Persistence of any non-target lesions and/or tumor marker level above the normal limits.

- PD: Unequivocal progression of preexisting lesions. Generally the overall tumor burden must increase sufficiently to merit discontinuation of therapy. In the presence SD or PR in target disease, progression due to unequivocal increase in non-target disease should be rare.
- Indeterminate: Progression has not been determined and one or more non-target sites were not assessed or assessment methods were inconsistent with those used at baseline.

New Lesions

The appearance of any new unequivocal malignant lesion indicates PD. If a new lesion is equivocal, for example due to its small size, continued assessment will clarify the etiology. If repeat assessments confirm the lesion, then progression should be recorded on the date of the initial assessment. A lesion identified in an area not previously scanned will be considered a new lesion.

Lesion Changes That May Be Transient

Potential exists for individual tumor lesions to develop necrosis, to cavitate, have a flare response to treatment or become otherwise difficult to evaluate for a period of time as the result of beneficial study treatment impact. For example, tumor necrosis, cavitation or flare may result in increase in overall size of individual lesions or unclear tumor margins prior to recovery to smaller lesions, development of scar tissue, or complete resolution. The true tumor measurements of lesions should be recorded but the conclusion of progressive disease may be suspended until continued assessment clarifies the nature of the tumor change. If repeat assessments indicate progression of disease, then PD should be recorded on the date of the first assessment giving the impression of progression. If repeat assessments indicate that the change was a process of transition, then NE (not evaluable) should be recorded during the period of transition, and PR or CR may be recorded for subsequent evaluations. The CRF will collect information on the observations during the period of transition to support the assessment conclusions.

Supplemental Investigations

If CR determination depends on a residual lesion that decreased in size but did not disappear completely, it is recommended the residual lesion be investigated with biopsy or fine needle aspirate. If no disease is identified, objective status is CR.

Best Objective Response

Target Lesions	Non-Target Lesions	New Lesion	Point in Time Response	Best Response
CR	CR	No	CR	CR and PR require
CR	Non-CR/Non-PD	No	PR	confirmation at least 4 weeks after first
PR	Non-PD	No	PR	observation
SD	Non-PD	No	SD	SD requires an on-study assessment after at least 6weeks on treatment. Unconfirmed PR or CR are reported as SD.
PD	Any	Yes or No	PD	
Any	PD	Yes or No	PD	
Any	Any	Yes	PD	

Patientive Progression

Patients requiring discontinuation of treatment due to worsening health status attributable to advancement of the malignancy under study but without objective evidence of disease progression should not be reported as PD on tumor assessment CRFs. This should be indicated on the end of treatment CRF as off treatment due to Global Deterioration of Health Status.

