3.2 Phase 2 Study

Following completion of the lead-in dose escalation evaluation, enrollment into the Phase 2 study will proceed.

The treatment arms included in this study are the following:

- 1. Glesatinib plus nivolumab.
- 2. Sitravatinib plus nivolumab.
- 3. Mocetinostat plus nivolumab.

For patients who have experienced progression of disease on or after treatment with a checkpoint inhibitor (CIT-experienced), enrollment into each treatment arm will be stratified by prior outcome of treatment with a checkpoint inhibitor:

- a. Clinical benefit (i.e., RECIST defined partial or complete response or stable disease for at least 12 weeks [-2 week window permitted for radiograph scheduling]) followed by radiographic progression of disease.
- b. No prior clinical benefit (i.e., radiographic progression of disease ≤ 12 weeks after initiation of treatment [+2 week window permitted for radiograph scheduling]).

Thus, the study will include 6 parallel evaluations of clinical activity of nivolumab combination regimens (Figure 3) in patients with prior treatment with a checkpoint

inhibitor. Patients enrolled in the lead-in dose escalation evaluation and receiving the dose of investigational study treatment chosen for the Phase 2 study will be included in the analysis of the Phase 2 endpoints. Patients who discontinue the study prior to the first on-study disease assessment for reasons other than disease progression may be replaced.

For patients without prior checkpoint inhibitor therapy (CIT-naïve), each investigational study treatment arm (i.e., glesatinib, sitravatinib, and mocetinostat) will be stratified according to PD-L1 status:

- a. Having tumor with no/low PD-L1 expression.
- b. Having tumor with high PD-L1 expression.

Tumor PD-L1 expression will be determined by the PD-L1 (28-8) companion diagnostics assay completed through the central laboratory. No/low PD-L1 expression is defined as positivity < 5% of tumor cells; high PD-L1 expression is defined as positivity $\ge 5\%$ of tumor cells. Tumor samples used to establish PD-L1 expression for eligibility must have been collected after the most recent systemic therapy.

Thus, the study will include 6 parallel evaluations of clinical activity of nivolumab combination regimens (Figure 3) in patients without prior treatment with a checkpoint inhibitor.

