Statistical Design Applied to CIT-Naïve with High PD-L1 Expression

The ORR using nivolumab in the population with non-squamous NSCLC having high PD-L1 expression is assumed to be 27% (p_0); thus this rate is considered uninteresting. The target ORR using the investigational agents in combination with nivolumab is 50% (p_1).

Stage 1 of enrollment will include approximately 17 evaluable patients. With exactly 17 evaluable patients at Stage 1, if at least 5 patients have Objective Responses, 27 additional evaluable patients will be enrolled, for a total sample size of 44 evaluable patients. If at least 18 Objective Responses are observed, further investigation may be warranted. If the true ORR is 27% (null hypothesis), the probability of early termination during the study is 0.50; the Type 1 error is equal to 0.0303 and the power is equal to 0.9018.

The exact stopping rules for all cohorts will be calculated based on the Predictive Probability Design, once the exact number of patients evaluable at Stage 1 is known. The aim is to get a minimum of 9 evaluable patients at Stage 1 for CIT-experienced and CIT-naïve with no/low PD-L1 expression cohorts and a minimum of 17 evaluable patients at Stage 1 for CIT-naïve with high PD-L1 expression cohort.

In order to be part of the clinical activity evaluable population, the patient must have at least one on-study disease assessment or discontinue from treatment for progressive disease prior to this assessment. Patients who discontinue treatment prior to the first on-study disease assessment for an AE, toxicity, or withdraw consent are considered non-evaluable for disease assessment. These patients will not be part of the clinical activity evaluable population.

[figure not shown]
Expansion Beyond Stage 2

[figure not shown]
The original protocol provided that if results in any strata were of high interest for efficacy, enrollment might be expanded to as many as 100 patients total in each cohort to narrow the 95% Confidence Interval (CI) around the ORR point estimate. Protocol Amendment 3 (Version 4.0) eliminates enrollment expansion beyond Stage 2 except in the sitravatinib segment of the study enrolling patients with CIT-experience.

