6.5 Patient Discontinuation/Withdrawal

Patients may discontinue from study treatment or from study follow-up at any time at their own request, or they may be discontinued at any time at the discretion of the Investigator or Sponsor for safety, behavioral reasons, or the inability of the patient to comply with the protocol required schedule of study visits or procedures at a given study site.

Criteria that may be used to discontinue patients from receipt of study medication will include, but will not be limited to:

- Objective disease progression according to RECIST 1.1 as determined by the Investigator (patients who may derive clinical benefit may continue on treatment at the discretion of the Investigator);
- Global deterioration of health status requiring discontinuation;
- Adverse event;
- Significant protocol violation;
- Lost to follow-up;
- Refusal for further treatment;
- Study termination by Sponsor;
- Death.

Reasons for discontinuation from study follow-up may include:

- Study terminated by Sponsor;
- Lost to follow-up;
- Refusal for further follow-up for survival;
- Death.

If a patient does not return for a scheduled visit, every effort should be made to contact the patient. At least 2 attempts should be made to contact the patient, and each attempt should be recorded in the source documents. In any circumstance, every effort should be made to document patient outcome, if possible. The Investigator should inquire about the reason for withdrawal, request that the patient returns for a final visit, and if applicable, follow-up with the patient regarding any unresolved adverse events.

If the patient withdraws from the study treatment and also withdraws consent for disclosure of future information, no further evaluations should be performed, and no additional data should be collected. The Sponsor may retain and continue to use any data collected before such refusal for further follow-up.

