9.3.2 Clinical Activity Evaluable Population

In order to be considered eligible for the clinical activity evaluable population, the patient must have at least one on-study disease assessment or discontinue from treatment for progressive disease. Patients who discontinue treatment prior to the first on-study disease assessment for an AE, toxicity, or withdraw consent are considered non-evaluable for disease assessment and will not be part of the clinical activity evaluable population.

This population will be used to present tumor responses as well as to make decision on the Predictive Probability design.

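### Patients who fail from the cancer before any on-study scan have no route into the evaluable population, so stage decisions made on it do not have the stated Type 1 error

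*Protocol*

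**What the plan says.** **How the reason is recorded.** Protocol Appendix 4 says that patients who come off treatment because the cancer has made them worse, but "without objective evidence of disease progression should not be reported as PD on tumor assessment CRFs". For the end-of-treatment form it adds: "This should be indicated on the end of treatment CRF as off treatment due to Global Deterioration of Health Status". Section 6.5 lists "Objective disease progression according to RECIST 1.1 as determined by the Investigator" and "Global deterioration of health status requiring discontinuation" as separate reasons for stopping study medication, and lists death as another.

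**Who is evaluable.** Under protocol 3.2 a patient "must have at least one on-study disease assessment or discontinue from treatment for progressive disease prior to this assessment". Section 9.3.2 gives essentially the same two routes and then names who is out: "Patients who discontinue treatment prior to the first on-study disease assessment for an AE, toxicity, or withdraw consent are considered non-evaluable for disease assessment". Global deterioration and death are not on that list. SAP 4.1.3 keeps the PD route. SAP 7.3 has no such route and requires both a baseline and a post-baseline tumor assessment.

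**Where it is used.** Protocol 9.3.2 and SAP 10 apply the Predictive Probability rule to the evaluable population, and the stage sizes are stated in evaluable patients. Protocol 9.3.1 says instead that the mITT is used for decisions to expand to the next stage. Supportive ORR (SAP 11.1.6.1) and CBR (SAP 11.1.6.2.1) are also presented on the evaluable population.

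**Replacement.** Protocol 3.2 adds: "Patients who discontinue the study prior to the first on-study disease assessment for reasons other than disease progression may be replaced".

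**The concern.** The PD route in 3.2 and 9.3.2 appears meant to keep early treatment failures in the denominator. It does not reach the patient who deteriorates or dies from the cancer and is never scanned. That patient has no on-study assessment and no recorded PD, so neither protocol route applies, and SAP 7.3 excludes them for want of a post-baseline assessment. Yet they are not among the reasons listed as non-evaluable, so the protocol simply leaves them unclassified.

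Such a patient is a certain non-responder. The null rates of 5% and 27% are given for the whole stratum, but the stage counts are in evaluable patients. Each omitted failure is made up by another evaluable patient. The rule then sees a higher response rate than the stratum has, early stopping becomes less likely, and the chance of a false go exceeds the stated figure. Supportive ORR and CBR on the evaluable population are raised in the same way.

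**Working it through.** **Inputs** (protocol 9.1.2; SAP 6.2.1.2 and 6.2.1.3)
- 9/17 design: p0 = 5%, p1 = 30%; continue with at least 1 response in 9; positive with at least 3 in 17.
- 17/44 design: p0 = 27%, p1 = 50%; continue with at least 5 in 17; positive with at least 18 in 44.
- Type 1 error is constrained to below 0.05.
- q, the share of treated patients never scanned because of early deterioration or death from the cancer, is an assumption. The documents give no value.

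**Formulas.** With n1 patients and threshold r1 at Stage 1, and n patients and threshold r at the end:
- early termination = P(X1 < r1)
- probability of a positive result = sum over x ≥ r1 of P(X1 = x) × P(X2 ≥ r − x), where X2 is binomial on n − n1 patients.

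**Reproducing the plan, 9/17 at 5%.** Early termination = 0.95^9 = 0.6302. Type 1 error has three parts:
- x = 1: 0.2985 × 0.0572 = 0.0171
- x = 2: 0.0629 × 0.3366 = 0.0212
- x ≥ 3: 0.0084

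The sum is 0.0466 after rounding, as stated. Power is 0.9045, as stated. The same formulas for 17/44 give early termination 0.4977, Type 1 error 0.0303 and power 0.9018, matching the stated 0.50, 0.0303 and 0.9018.

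**Effect of omission.** Suppose the true rate among all treated patients is p0 and a share q, all non-responders, is left out while the evaluable count is still filled. The rule then sees p0/(1 − q). At q = 10% this is 0.05/0.90 = 5.56% and 0.27/0.90 = 30.0%.

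| q (assumed) | 9/17: rate seen | early termination | Type 1 error | 17/44: rate seen | early termination | Type 1 error |
|---|---|---|---|---|---|---|
| 0 | 5.00% | 0.630 | 0.0466 | 27.0% | 0.498 | 0.0303 |
| 2% | 5.10% | 0.624 | 0.0490 | 27.6% | 0.477 | 0.0367 |
| 5% | 5.26% | 0.615 | 0.0529 | 28.4% | 0.445 | 0.0487 |
| 10% | 5.56% | 0.598 | 0.0604 | 30.0% | 0.389 | 0.0778 |
| 15% | 5.88% | 0.580 | 0.0693 | 31.8% | 0.330 | 0.1228 |
| 20% | 6.25% | 0.559 | 0.0801 | 33.8% | 0.269 | 0.1904 |

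Type 1 error reaches 0.05 when the rate seen is 5.144% (9/17) or 28.50% (17/44). That is q = 1 − 5/5.144 = 2.8%, about one treated patient in 36, and q = 1 − 27/28.50 = 5.3%, about one in 19. If the same patients are kept as non-responders, the q = 0 row applies.

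**The case against.** Several points narrow the concern, and most of them stand.

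- **The PD route is not shown to be empty.** A reader might infer that nobody can enter by it. But objective PD can appear on an unscheduled scan before the first scheduled one. If any post-dose scan counts as on-study, as SAP 8.2 suggests, the route is redundant instead. On either reading it still misses the patient who is never scanned.
- **Not every early clinical progressor is lost.** Protocol 3.2 and 7.1 keep scans due after treatment stops, until objective progression or new anti-cancer therapy. A patient alive at week 8 on no new therapy should still be scanned and would then be evaluable. So q covers only those never scanned, a smaller group than all who stop early.
- **The replacement sentence does not plainly cover them.** It concerns leaving the study, whereas section 6.5 lists global deterioration only as a reason for stopping study medication. It also says progression without the word objective. Death is on both lists in 6.5, so a cancer death is left ambiguous. The calculation does not need this sentence, because stage sizes are already counted in evaluable patients.
- **Protocol 9.3.1 names the mITT.** Under it these patients stay in and the problem does not arise. But protocol 9.3.2, SAP 10 and the design wording all point to evaluable patients, and the conflict is unresolved.
- **SAP 7.3 excludes them whatever the form says.** This is true. Restoring the PD route of SAP 4.1.3 would still leave them out, because their recorded reason is not PD.
- **Stopping rules are to be recalculated from the actual evaluable number.** The 9/17 and 17/44 designs are therefore reference cases. Recalculating on evaluable patients does not bring the omitted failures back.

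**Conclusion.** Wrong as written, within limits. Following SAP 7.3 and SAP 10 literally removes certain non-responders from the stage-decision denominator. The stated Type 1 errors and early-termination probabilities then do not hold as rates for the treated population. The direction is certain. The size depends on q, and the results assume that stage decisions use the evaluable population and that its counts are filled by further enrollment. At q = 5% the Type 1 errors are 0.053 and 0.049, so the effect is modest. At q = 10% they are 0.060 and 0.078.

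A reader might infer that the trial's main result is biased. The documents do not support that: SAP 11.1.6.1 runs the primary ORR analysis on the FAS and counts patients who cannot be assessed as non-responders. Nor would new wording change the sitravatinib CIT-experienced expansion, which protocol 3.2 bases on the June 2018 results. For those strata the change bears on how the go decision is described and on the supportive tables.

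**What to change.** 1. Name one stage-decision population, reconciling protocol 9.3.1 with protocol 9.3.2 and SAP 10.
2. In protocol 3.2 and 9.3.2 and in SAP 4.1.3 and 7.3, use a single evaluable definition. It should count as an evaluable non-responder any patient with no on-study assessment who stops treatment for Global Deterioration of Health Status attributed to the malignancy, or who dies of the disease.
3. State in protocol 3.2 that these patients are not replaced.

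With these patients kept in, the stated operating characteristics no longer suffer from this omission. The cost is wording only: the end-of-treatment reason is already on the CRF, and SAP 4.0 provides for a final SAP version before database lock. The downside is a slightly lower evaluable-population ORR and fewer replacements.
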